Solriamfetol (trade name Sunosi), is a norepinephrine-dopamine reuptake inhibitor available in 75mg and 150mg tablets for oral administration during the day. Solriamfetol's primary indication is to treat excessive daytime sleepiness (EDS) in patients diagnosed with OSA or Narcolepsy. It binds to the dopamine transporter and the norepinephrine transporter with affinities (K_i) of 14.2 μ M and 3.7 μ M, respectively), does not undergo significant metabolism in humans, and has a T_{max} of ~2 hours (range 1.25–3.0 hours) and a $T_{1/2}$ of ~7.1 hours. The pharmacokinetic profile of solriamfetol, along with the absence of active metabolites, makes it unlikely that there are accumulation effects with multiple doses over days. See the attachment for a copy of the package insert for solriamfetol.

Solriamfetol will be provided by Axsome Pharmaceuticals (no cost), and managed by, the Investigational Drug Services of the University of Pennsylvania. An over encapsulation technique will be used to ensure that the drug doses and placebo formulations appear identical. The first five participants will be enrolled slowly to observe whether any adverse responses occur (e.g., taking longer to fall asleep after medication administration at 2pm) that would necessitate protocol modifications, for instance to the timing of medication dosing, if not amount.

Solriamfetol or placebo will be administered at 2pm daily for 4 weeks. Dosage will (for all subjects) start at 75mg. This dosage was chosen through weighing up the need to extend wake/delay bedtime to consolidate sleep and improve sleep continuity (necessitating a later timing of dose than typical), without inadvertently enhancing wake to the point where it extends sleep latency. Rather than downwardly titrate the medication, the timing of dosing will be altered where required (for example, timing advanced to 1pm or 12pm). Changes in dose timing will occur when the study staff (therapist, PI, and medical collaborator) deem it to be optimal (i.e., in response to extended sleep latency). Subjects in the SRFT + CBT-I arm will also be eligible for changes in dose timing if they report being unable to adhere to the prescribed time to bed (PTTB) component of CBT-I. As noted above, medication use will also include a 1-week placebo run-in and a 3-week placebo "run-out" (eight weeks' total). The timing of the first administration of SRFTL will (for those receiving CBT-I) align with the start of sleep restriction (Session 2).

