3.2 Secondary Objectives (if applicable)

Assess the effects of solriamfetol on daytime sleepiness, fatigue, adherence with “sleep rescheduling”, and on daytime performance

4. Investigational Plan

All subjects will be monitored for 2 weeks prior to treatment, for 8 weeks during treatment, and for 2 weeks following treatment. Additionally, subjects will complete two questionnaires complete two questionnaires (Insomnia Severity Index [ISI] and Retrospective Sleep Continuity Assessment Questionnaire [RSCAQ]) 3 months after completing treatment.3 months after completing treatment. Subjects receiving solriamfetol will take medication at 2pm daily for 4 weeks. Medication use will also include a 1-week placebo run-in and a 3-week placebo “run-out” (8 weeks’ total). Note: This design was used for our prior trials of CBT-I with wake promoting medications. Subjects receiving CBT-I will have 8 weekly

sessions (up to 90 minutes in duration). Daily sleep diaries will be administered to assess for differences in sleep continuity between conditions and over time. Self-report weekly assessments will also be administered and will include standard retrospective measures of insomnia (ISI), sleepiness (Epworth Sleepiness Scale, ESS), depression (PHQ-9), fatigue (Functional Assessment of Chronic Illness Therapy – Fatigue Scale [*FACIT-Fatigue*]), PROMIS-Short Form 7a, and Brief Fatigue Inventory [BFI]), treatment acceptability (MITAS)), and daytime function (Functional Outcomes of Sleep-10 item, FOSQ-10). Daytime function will also be objectively assessed daily via Ecological Momentary Assessment and at the end of baseline treatment, and post treatment periods using a PVT phone-based app. Self-report assessments will be accomplished on-line via RedCap software and subjects will also be asked to complete weekly and monthly questionnaires via Hypknowledge (a PHT Penn Health Tech Clinical Research Tool) site.

Treatment Regimen (as noted above)

The first five participants will be enrolled slowly to observe whether any adverse responses occur (e.g., taking longer to fall asleep after medication administration at 2pm) that would necessitate protocol modifications, for instance to the timing of medication dosing, if not amount.

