Session 2: data acquisition and delivery of sleep restriction therapy & stimulus control instructions

Session 3: review of sleep hygiene

Session 4: management of non-adherence and/or time-in-bed titration only

Session 5: cognitive therapy [de-catastrophization]

Session 6: management of non-adherence and/or time-in-bed titration only

Session 7: management of non-adherence and/or time-in-bed titration only

Session 8: review of treatment progress and relapse prevention.

All treatment will be delivered by a single master therapist ([name] PhD CBSM). [name] has more than 27 years’ experience with CBT-I, he is one of the authors of our published treatment manual (1), and he is also a co-author of a second CBT-I treatment manual (2). He was a consultant for the VA’s rollout of CBT-I, he jointly conducts the Penn 3-day Basic and Advanced CBT-I courses, and he regularly conducts on-site one-day CBT-I workshops. As a final testament to his expertise, he was one of the first individuals to be certified in behavioral sleep medicine and one of the first to receive the SBSM’s Distinguished Career Achievement Award.

5. General Design

A double blind 2x2 mixed model design. The two factors will be 1) treatment (+/- solriamfetol and +/- CBT-I) and 2) Time (pre-post assessment, with additional follow-up data). Patients with insomnia will be randomly assigned to treatment condition.

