As noted above, side effects will be assessed in several ways: daily assessments via the sleep diaries and weekly evaluation with a medical symptom checklist (52 symptoms where positive endorsements allow subjects to rate their average severity and number of days affected).

10. Statistical Plan

k. Primary Endpoint

The primary endpoint is total wake time (time spent awake in bed) at the end of post-treatment, as measured via a web based self-report Sleep Diary.

I. Secondary Endpoints

1. Patients treated with CBT-I will have significantly greater improvements in sleep continuity from baseline to post-treatment compared to patients not administered CBT-I.
2. Patients treated with CBT-I in combination with solriamfetol will have significantly greater improvements in sleep continuity from baseline to post-treatment compared to patients treated with CBT-I alone.
3. Exploratory hypotheses: Patients treated with CBT-I in combination with solriamfetol will have significantly greater adherence with sleep restriction (i.e., sleep rescheduling, prescribed time to bed [PTTB]) and on daytime performance measures (e.g., ESS, FSS, etc.) compared to CBT-I alone.

m. Sample Size and Power Determination

To detect a clinically significant difference in self-reported total wake time of 30 minutes between the four treatment groups at the end of post-treatment using an ANOVA test, this study will require 10 subjects per group x 4 groups = 40 treatment completers. These calculations assume a standard deviation in total wake time of 19 minutes, with 80% power to detect the clinically significant change at an alpha level of .05. A total of 60 subjects will be recruited to obtain a sample of 40 subjects that complete the study due to attrition.

n. Statistical Methods

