Primary analyses will be conducted on an intention to treat basis and the trial conducted and reported according to CONSORT guidelines. Variable distributions will be examined to investigate homoscedasticity, outliers and normality, and corrected where appropriate using data transformations. The primary analysis is a 4(condition: +/- solriamfetol and +/- CBT-I) x 2(time: pre- and post-treatment) mixed ANOVA on absolute and percent change in total wake time ([TWT], time spent awake per night). If the interaction between condition and time is significant, Dunnett multiple comparisons will be conducted to further investigate differences in TWT between active treatment conditions versus the control condition to test Hypotheses 1-3. These analyses will be unadjusted in the first instance and then adjusted for covariates (primarily, age and sex).

An interim unadjusted analysis as per above will be conducted after 50% of the target sample have completed post-treatment (i.e., when N=20).

Secondary analyses include examining the interaction between treatment condition and time on other outcomes, including sleep continuity assessed via Sleep Diary (SL, WASO, EMA, TST, SE), insomnia (ISI), daytime sleepiness (ESS and KSS), fatigue (FSS and modified KSS), and daytime function (FOSQ-10, POMS, and PVT). Additionally, compliance to the medication (adherence to daily pill administration, as assessed via blister packs) and to sleep restriction (adherence to prescribed time to bed) will be investigated as covariates.

i. Baseline Data

Baseline and demographic characteristics will be summarized by standard descriptive statistics (including mean and standard deviation for continuous variables such as age and standard percentages for categorical variables such as gender).

ii. Pharmacokinetic Analysis **N/A**

iii. Interim Analysis **N/A**

iv. Safety Analysis

Side effects and adverse events will be assessed in several ways: daily assessments via the sleep diaries, and with a weekly evaluation using a medical symptoms checklist (52 symptoms where positive endorsements allow subjects to rate their average severity and number of days affected),

An adverse event will be defined as 1) any behavioral or health complaint spontaneously reported during the study, 2) an above threshold score on the study clinical assessment instruments (ESS, PHQ-9, or GAD-7), and/or a 20% increase in the medical symptom check list scores (frequency or severity).

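### The secondary ESS analysis has no time levels of its own; on the only levels defined, pre-post, sleepiness is compared 3 to 5 weeks after the last active dose, although ESS is collected weekly.

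*Combined protocol and SAP*

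**What the plan says.** **Objective.** Section 3.2 sets the secondary objective: "Assess the effects of solriamfetol on daytime sleepiness, fatigue", together with adherence and daytime performance.

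**Analysis.** Section 10.n: "Secondary analyses include examining the interaction between treatment condition and time on other outcomes". The outcomes listed there include "daytime sleepiness (ESS and KSS), fatigue (FSS and modified KSS". No visit, week or set of time levels is given for them.

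**Definition of time.** The synopsis, section 5 (General Design) and section 7.b (Intervention Regimen) all give the second factor as "Time (pre-post assessment, with additional follow-up data". Section 10.n also gives time two levels, before and after treatment, but attaches them to the primary total wake time model.

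**Hypothesis.** The exploratory hypothesis (section 10, Secondary Endpoints, item 3) expects the combination to do better "on daytime performance measures (e.g., ESS, FSS, etc.) compared to CBT-I alone". Unlike items 1 and 2, it does not say that the change runs from baseline to post-treatment.

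**Treatment schedule.** Subjects are monitored "for 8 weeks during treatment, and for 2 weeks following treatment" (section 4). Active drug lasts 4 weeks, and "medication use will also include a 1-week placebo run-in and a 3-week placebo" run-out (sections 2 and 4).

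**Data collected.** Section 4: "Self-report weekly assessments will also be administered". The instrument table marks ESS, BFI, FACIT-F and PROMIS-SF 7a at pre, weekly and post. FSS, KSS and modified KSS are not in that table.

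**The concern.** The rationale in section 1 is that a wake-promoting drug may help patients who cannot accept the temporary sleepiness that CBT-I causes. The first active dose is deliberately timed to the start of sleep restriction at Session 2. Any relief from the drug would therefore be looked for in the active weeks. The only time levels the plan defines look before the drug starts and well after it stops.

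The Publication Plan says the study's main purpose is to obtain effect sizes. On pre-post levels, the effect size for ESS would be an off-drug one. A lasting indirect benefit through better-consolidated sleep could still appear there, but relief while taking the drug could not. A null result could be read as no relief, even though the data that bear on that question had been collected. If the team instead means to use the weekly values, the plan does not say which weeks or which contrast, and the choice stays open until the data are seen.

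**Working it through.** **1. Timeline (sections 2 and 4).** The plan's own total reproduces: 1 week run-in + 4 weeks active + 3 weeks run-out = 8 weeks.

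| Period | Treatment week |
|---|---|
| Placebo run-in | 1 |
| Active solriamfetol (or placebo) | 2–5 |
| Placebo run-out | 6–8 |
| Post-treatment monitoring | 9–10 |

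The last active dose is at the end of week 5. The exact day of the post assessment is not given. At the end of week 8 the gap is 8 − 5 = 3 weeks; at the end of week 10 it is 10 − 5 = 5 weeks.

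**2. Drug remaining.** The half-life is about 7.1 h (section 2.2).
- 3 weeks: 21 × 24 / 7.1 = 71 half-lives.
- 5 weeks: 35 × 24 / 7.1 = 118 half-lives.

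This shows clearance only. It does not exclude an indirect effect that outlasts the drug. If the drug acts only while it is taken, the expected pre-post drug difference is 0, whatever its on-drug size.

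**3. Follow-up does not help.** The 3-month assessment (section 5.4) collects the ISI and a retrospective sleep questionnaire, with no ESS or fatigue scale, and it is further from the last dose.

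**4. Data left unused by pre-post.** Weekly ESS gives four readings in weeks 2 to 5. A two-level time factor uses none of them.

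**5. Fatigue.** Section 10.n names FSS and modified KSS. Neither has a collection schedule, so no gap from the last dose can be calculated. The three weekly fatigue scales (BFI, FACIT-F, PROMIS-SF 7a) are not named in the analysis. KSS under sleepiness has the same problem. The timing calculation therefore applies to ESS alone.

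**6. Precision of an on-drug ESS contrast.** Group sizes are the plan's 10 completers per group. Assumptions not in the documents: ESS SD 4 to 5, and a common correlation ρ of 0.5 to 0.7 between any two readings of one person.

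Variance of the mean of four weekly readings, adjusted for baseline, in SD² units: v = (1 + 3ρ)/4 − ρ².
- ρ = 0.5: 0.625 − 0.25 = 0.375
- ρ = 0.6: 0.70 − 0.36 = 0.34
- ρ = 0.7: 0.775 − 0.49 = 0.285

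Standard error = SD × √(2v/n). The 95% half-width is t × SE, with t = 2.110 for 10 v 10 (17 df) and 2.030 for 20 v 20 (35 df: four arms and one covariate). Example, 10 v 10, SD 4, ρ = 0.5: 4 × √(0.75/10) = 1.095, and 2.110 × 1.095 = 2.31.

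| Contrast | SD | Half-width, ρ = 0.5 / 0.6 / 0.7 | Power for 3 points | Power for 2 points |
|---|---|---|---|---|
| 20 v 20 | 4 | 1.57 / 1.50 / 1.37 | 96 / 98 / 99% | 71 / 75 / 82% |
| 20 v 20 | 5 | 1.97 / 1.87 / 1.71 | 85 / 89 / 93% | 52 / 56 / 63% |
| 10 v 10 | 4 | 2.31 / 2.20 / 2.01 | 73 / 77 / 84% | 41 / 44 / 51% |
| 10 v 10 | 5 | 2.89 / 2.75 / 2.52 | 54 / 58 / 66% | 28 / 30 / 35% |

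Power is from the noncentral t at two-sided 0.05. The 2- and 3-point effects are illustrations, not plan values. If 3 points of relief occurred only with CBT-I, the 20 v 20 average would be 1.5 points, with power of 33 to 58% over the same range.

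**The case against.** **The plan does not say the ESS comparison is pre-post.** This stands. The two-level definition in section 10.n belongs to the primary model, and the secondary sentence does not repeat it. Hypothesis 3 lacks the baseline to post-treatment wording. Section 9.g counts weekly questionnaires as part of the efficacy evaluation, and nothing rules out weekly data. A reader might infer that the sponsor chose an off-drug comparison for sleepiness; the documents do not support that. They show that the levels are unstated and that the only ones available to inherit are pre-post. The gap remains on either reading, because no week and no on-drug contrast is named.

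**The fatigue comparison is also 3 or more weeks off drug.** A reader might infer this too, but the named fatigue scales have no schedule. What stands for fatigue is a mismatch between the scales analysed and those collected.

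**The run-out is deliberate.** Section 4 says the design was used in the group's earlier trials. An off-drug end-state contrast is legitimate and should stay. It answers a different question from relief during treatment.

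**Adverse event rules already watch ESS.** Section 10.n.iv flags individual scores above a threshold. It does not estimate a mean difference between arms.

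**The groups are small and the hypothesis exploratory.** Both are true. They limit what the contrast can establish and argue for estimates with intervals, but not for leaving the on-drug weeks unanalysed.

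**Conclusion.** The point holds for ESS, and conditionally: if the only defined time levels are applied, sleepiness is compared 3 to 5 weeks after the last active dose, and the contrast cannot show a direct on-drug effect. The gap follows from the plan's own schedule. That pre-post applies to ESS is an inference. For fatigue, the documents support only that a collected scale needs to be named.

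It would go too far to say that the trial cannot study on-drug sleepiness, since the weekly data are scheduled, or that a pre-post difference must be zero, since an indirect effect could persist. How far pre-post would also understate the temporary sleepiness from CBT-I cannot be fixed from the documents, because they do not give its course after sleep restriction begins.

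The precision figures rest on the assumed ESS SD and correlation. The primary total wake time analysis and the sample size are unaffected. This is a cheap improvement to a secondary analysis.

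**What to change.** In section 10.n:

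1. State the time levels for the secondary outcomes.
2. Add a baseline-adjusted repeated-measures model of weekly ESS with week as the time factor. Fit the same model to one weekly fatigue scale that is collected, such as FACIT-F or BFI, and name that scale in the analysis.
3. Prespecify solriamfetol versus placebo on the mean of treatment weeks 2 to 5, overall (20 v 20) and within CBT-I (combination versus CBT-I alone, 10 v 10). The first matches the secondary objective, the second hypothesis 3.
4. Keep pre-post as the off-drug end-state contrast, labelled as such.
5. Report all of these as estimates with 95% confidence intervals. CBT-I alone versus placebo without CBT-I over the same weeks is optional and descriptive; no stated hypothesis calls for it.

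For ESS and the chosen fatigue scale this needs no new visits, patients or instruments. The cost is plan wording, one further model per scale, and two more contrasts per scale (three with the optional one). Precision is modest, especially within CBT-I, so these contrasts should not be read as confirmatory tests.

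### The secondary analysis list names FSS, KSS and modified KSS, which no schedule contains; it names none of the three scheduled fatigue scales, and POMS has no Post mark.

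*Combined protocol and SAP*

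**What the plan says.** Fatigue is in the protocol title and in the secondary objective (Section 3.2): "Assess the effects of solriamfetol on daytime sleepiness, fatigue, adherence with" and so on. Section 10, Statistical Methods, introduces the secondary analyses with "Secondary analyses include examining the interaction between treatment condition and time on other outcomes, including sleep continuity assessed via Sleep Diary" and, after the diary variables, continues: "insomnia (ISI), daytime sleepiness (ESS and KSS), fatigue (FSS and modified KSS), and daytime function (FOSQ-10, POMS, and PVT". The primary model in the same section defines time as pre- and post-treatment. FSS is also given as an example measure in the exploratory hypothesis, in Section 5.6.2 and again under Secondary Endpoints in Section 10.

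Section 4 (Investigational Plan) describes collection. For fatigue it lists FACIT-Fatigue, "PROMIS-Short Form 7a, and Brief Fatigue Inventory [BFI"; for sleepiness, ESS only. It includes "daytime function (Functional Outcomes of Sleep-10 item, FOSQ-10" and MITAS among the weekly self-report measures. PVT is to be done "at the end of baseline treatment, and post treatment periods using a PVT phone-based app". Two further sources are mentioned without their content: "Daytime function will also be objectively assessed daily via Ecological Momentary Assessment", and "subjects will also be asked to complete weekly and monthly questionnaires via Hypknowledge".

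The Table of Instruments has 15 rows and columns for Pre, Daily, Weekly, Post and 3-month follow-up. BFI, FACIT-F and PROMIS-SF 7a are each marked Pre, Weekly and Post. POMS and FOSQ-10 are marked Pre and 3 months, MITAS 3 months only, and PVT Daily only. Sections 4, 5.4 and 6.d restrict the 3-month contact to ISI and RSCAQ.

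**The concern.** The analysis list and the collection schedule describe different sets of instruments. The mismatch covers all of fatigue: the two measures to be analysed have no documented data, and the three measures with documented data have no named analysis. Someone must later decide which scale carries the fatigue result, and nothing in the plan says that this happens before results are seen.

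The timing of that decision matters here. Statistical Methods describes an interim analysis at N=20, although the Interim Analysis item below it says not applicable. The Publication Plan foresees a report if results are significant with 5 to 8 subjects per condition. No multiplicity control is stated for the secondary outcomes.

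POMS raises a separate problem. If the table is followed, POMS can be compared from baseline to 3 months but cannot enter a pre/post condition-by-time model. An end-of-treatment value that was not collected cannot be recovered later.

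**Working it through.** No figure of the plan is in dispute, so the check sets the documents side by side. The table below takes the 8 non-diary outcomes in Statistical Methods and compares them with the two places that describe collection.

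| Named outcome | Table of Instruments | Section 4 text | End-of-treatment value documented? |
|---|---|---|---|
| ISI | Pre, Weekly, Post, 3 months | weekly | yes |
| ESS | Pre, Weekly, Post | weekly | yes |
| KSS | no row | not named | no |
| FSS | no row | not named | no |
| modified KSS | no row | not named | no |
| FOSQ-10 | Pre, 3 months | weekly | yes, from the text only |
| POMS | Pre, 3 months | not named | no |
| PVT | Daily | end of periods | yes |

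**Outcomes without a documented value.** By table marks alone, 2 of 8 have both Pre and Post (ISI, ESS), 3 have no row, 2 have Pre but no Post (FOSQ-10, POMS) and 1 is Daily only (PVT): 2 + 3 + 2 + 1 = 8. That count is too strict, because a Daily or Weekly mark can also supply pre and post values; the sleep diary behind the primary endpoint is itself marked Daily only. Section 4 documents FOSQ-10 and PVT, so 8 − 2 − 2 = 4 remain: FSS, KSS, modified KSS and POMS.

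**Weekly measures in Section 4.** These are ISI, ESS, PHQ-9, FACIT-Fatigue, PROMIS-SF 7a, BFI, MITAS and FOSQ-10, which makes 8. None is FSS, KSS or modified KSS.

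**Fatigue.** Planned for analysis: FSS and modified KSS. Scheduled: BFI, FACIT-F and PROMIS-SF 7a. The two sets share 0 instruments.

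**3-month contact.** The table marks 5 instruments (ISI, RSCAQ, FOSQ-10, POMS, MITAS); the text allows 2 (ISI, RSCAQ). The 3 extra marks conflict with the text and may be Post marks in the wrong column.

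**What the open choice could cost.** Suppose each of the three scheduled scales were tested at .05 and there were no true effect on any of them. The chance of at least one significant result would be 5% if the scales were perfectly correlated and 1 − 0.95³ = 1 − 0.857 = 14.3% if they were independent. The documents give no correlations, so these two cases are assumptions that bracket the range.

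**The case against.** The strongest objection is that absence from the schedules proves little. Section 4 introduces its weekly measures with open wording, and its list is demonstrably incomplete: the Medical Symptom Checklist is weekly elsewhere but missing there. GAD-7 is used for exclusion and for defining adverse events but has no table row. The content of the momentary assessment and of the Hypknowledge questionnaires is not given, and the table has no monthly column. KSS items could sit in either source. This stands as a limit: the three scales are undocumented, not shown to be uncollected. It does not remove the mismatch, because no section links FSS, KSS or modified KSS to any of these sources.

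The analysis list is also open-ended, so the scheduled fatigue scales are unnamed rather than excluded. That is true, but an open list is what leaves the choice of scale undecided.

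The POMS point rests on the column of one mark in a table read from a PDF. Every row checked had the same number of fields as the header, which supports the reading but does not prove it. If the mark was meant for Post, the table still needs correcting. A shifted column cannot explain rows that do not exist. The documents also do not define Post exactly, and 2 weeks of monitoring follow treatment.

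Finally, only secondary and exploratory outcomes are involved, and the Publication Plan says that effect sizes are the main aim. Reporting all three fatigue scales would fit that aim. This limits the weight of the point, but the plan also promises inferential tests of these outcomes, and for those the instrument should be fixed in advance.

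**Conclusion.** The concern holds. Three named outcomes (FSS, KSS, modified KSS) are in no schedule, none of the three scheduled fatigue scales is named in the statistical plan, and POMS has no Post mark. Together, 4 of the 8 named non-diary outcomes lack a documented end-of-treatment value. The conclusion assumes that the table columns were read correctly and that no unlisted questionnaire supplies the missing scales. If one does, the error lies in the schedule rather than in the analysis list, and the documents still have to be reconciled.

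The primary analysis of total wake time is untouched, and fatigue can be tested from the three scheduled scales. This should be corrected, but it does not threaten the main result.

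**What to change.** 1. Confirm which instruments are collected, including the content of the momentary assessment and of the weekly and monthly Hypknowledge sets.
2. If FSS, KSS and modified KSS are collected, keep them and add them to the Table of Instruments with pre and post time points.
3. If they are not, replace FSS and modified KSS with the scheduled scales in Section 5.6.2, in Section 10 Secondary Endpoints and in Statistical Methods, and drop KSS, leaving ESS for sleepiness. Name one of BFI, FACIT-F or PROMIS-SF 7a as the fatigue outcome, with the others supportive, before any look at outcome data by condition.
4. Mark POMS and FOSQ-10 at Post.
5. Make the 3-month list, the FOSQ-10 and MITAS timing and the PVT frequency agree between Sections 4, 5.4 and 6.d and the table.

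The cost is wording, plus at most one or two online questionnaires at the post-treatment assessment. If the table reflects current practice and FOSQ-10 or MITAS is instead settled as weekly, participants also receive those weekly forms. Keeping the table timing with an added Post mark avoids that burden.
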